## 3C.7. Outcome Measures

**3C.7.1. Measure of Primary Outcome Variable: IID Lockout Events.** The primary outcome

measure will be frequency of IID lockout events from baseline to 9-month follow-up post-randomization, collected from the Santa Fe DWI program database for each first-time DWI offender participant. Marques, Voas and colleagues have demonstrated in a series of investigations that frequency of lockout events strongly predicts DWI recidivism over time, and as such, IID lockout events are an important and useful proxy measure for DWI recidivism. Given the length of time necessary to accumulate DWI recidivism data (average length of time varies across locales and can be between 2 and 8 years), IID lockout events provide a direct and accessible measure of DWI recidivism within the two-year project timeline.

**3C.7.2. Measures of Secondary Outcome Variables and Mediators.** Alcohol use by the DWI offender, a secondary outcome, will be assessed at baseline, 3-month follow-up, and 9-month follow-up with versions of the Form 90 adapted for online assessment for the CFMs (Form 90-ACS) and first-time DWI offenders (Form 90-AF). The Form 90 measures produce detailed quantity and frequency measure of alcohol use for the first-time offender that are validated by the CFM reports. Family functioning will be assessed at baseline, 3-month follow-up, and 9-month follow-up, as potential mediators of *B-SMART* effects, with DWI offenders and CFMs with three measures: (1) Family Environment Scale – Cohesion and Conflict subscales assesses offender and CFM perceptions of positive and negative family functioning; the two subscales selected are strongly associated with treatment outcome; (2) Family Communication Scale from FACES-IV assesses perception of quality of communication in the family; (3) Pleasant Events Schedule (adapted) assesses shared positive activities within a family. These three measures are also being used in the B-FIT study, allowing for comparison of outcomes across the two studies.

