## STATISTICAL ANALYSIS PLAN

### Sample Size Determination

The sample size for the randomized trial in the Phase II research is designed to provide sufficient information for Phase III commercialization. The sample size assumes the counts of interlocks are Poisson distributed. We have assumed 4 interlocks over 9 months in the control arm or a rate of 0.44 per month for each DWI offender. In the *B-SMART mobile web app* group, we have assumed a reduction of 40% from 0.44, resulting in a rate of 0.27 per month. The null hypothesis is that the ratio of these two rates is 1.0 versus 0.6. Assuming a Type I error of 0.05 (2-sided), 90% power, sample size is only 27 DWI offenders per group. However, if the rate is higher up to 1 per month, the sample size required declines since the percent reductions yield wider absolute differences in the rates. We also are keen to know the reductions achievable with the *B-SMART* group, so we evaluated the sample size with regards to other effect sizes. In a Cochrane meta-analysis reported the impact of IIDs to reduce risk by 64%, but with a confidence interval that ranged from 76% to 37%. In the proposed trial, we have two treatment groups and may see less impact than that in the meta-analysis. Thus, a sample size of 119 DWI offenders per group will allow for 90% power with a comparison of 0.44 to 0.36 or approximately a 20% reduction in interlocks. We will adjust for an expected 15% attrition and this sample size also has sufficient sample size to evaluate the impact in various gender and ethnic subgroups. Thus, we propose to randomize 150 DWI offenders and 150 CFMs to each arm of the trial.

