**Mediation Analysis for Hypothesis 2.** To address the predicted mediation effects of family function on improving the effect of the *B-SMART mobile web app* in Hypothesis 2, we will assess a formal effect on predicting fewer IID lockout events. Mediation will be tested by applying regression techniques from Judd and Kenny and elaborated by MacKinnon, with significance of mediation determined via interval estimation using bootstrapping. Ratio of indirect to total effects will estimate the proportion of the effect mediated. The primary mediational analysis will rely on temporal order of the posttests by examining the effect of *B-SMART* on change in the mediators from baseline to 3-month follow-up and in turn their association with changes in the IID lockout events from baseline to the 9-month follow-up and from 3- to 9-month follow-up.

**Ancillary Analysis of Moderators.** Potential moderators (see 3C.7.3) will be tested at  $p=.05$  (2-tailed) unadjusted for multiple tests. For Hypothesis 1, they will be added as interactions by condition in a manner similar to regression testing for effect modification. Gender is included to probe differences by sex of student and employee. For Hypothesis 2, we will explore if improvements in IID lockout events produced by increases in family function by different participant groups (gender, ethnicity, etc.), using moderated mediational analyses. Moderation effects must be large to be detected, so these are ancillary tests.

**Ancillary Analysis of the *B-SMART Mobile Web App* Exposure.** The same mediational analysis techniques described in 3C.8.4 will be used to explore the relationship of exposure to the *B-SMART mobile web app* and pre-post changes in IID lockout events. Summed scores on exposure will be calculated from the SQL database (e.g., time on app, number of visits to the app, etc.) to assess intervention exposure.

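### H2 prespecifies no mediator–lockout confounders, so if the app moves family scores, baseline offender severity can create, mask or reverse an apparent indirect effect

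*Combined protocol and SAP*

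**What the plan says.** H2 is one of the trial's two formal hypotheses. Its test appears in the SAP under Mediation Analysis for Hypothesis 2, and in substance also in protocol section 3C.8.3 and in the statistical design attachment (item 4.4). It uses regression-based mediation with a bootstrap interval and reports a proportion mediated. It relies on the order of the assessments: the app's effect "on change in the mediators from baseline to 3-month follow-up and in turn their association with changes in the IID lockout events", over baseline to 9 months and over 3 to 9 months.

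No covariate is named for the mediator regression or the lockout regression. Covariates are mentioned in two other places, both in the Outcome Analysis Plan. Sex, ethnicity and age are given as examples of covariates for the lockout Poisson regression. Baseline imbalances between arms are listed as something that might be adjusted for.

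The variables needed for adjustment exist. Section 3C.7.2 states: "Alcohol use by the DWI offender, a secondary outcome, will be assessed at baseline, 3-month follow-up, and 9-month follow-up". It also states: "Family functioning will be assessed at baseline, 3-month follow-up, and 9-month follow-up, as potential mediators". Lockout counts are obtained only at the 9-month point (section 3C.6.1), so the plan provides no pre-randomisation count that could stand in for severity.

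**The concern.** Randomisation protects the link from app to family score. It does not protect the link from family score to lockouts. A lockout is an alcohol-positive breath test, so offenders who drink more should have more of them. Drinking severity may also affect how a family's scores move over three months. The Phase I interviews (section 3C.1.3) noted that family members' outlook differed according to whether the offender still had a drinking problem. Temporal order does not remove this, because severity precedes both the family change and the lockouts. Checking arms for imbalance does not remove it either, because the confounding operates within arms even when the arms are perfectly balanced.

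At stake is the trial's claim about mechanism. A significant indirect effect could reflect a real family pathway, or family change acting only as a marker of severity. A null result could hide a real pathway.

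**Working it through.** **1. The plan's own figures, which supply the inputs.** The documents give a sample size for H1 only. The inputs are: "We have assumed 4 interlocks over 9 months in the control arm or a rate of 0.44 per month for each DWI offender"; "we have assumed a reduction of 40% from 0.44, resulting in a rate of 0.27 per month"; "Assuming a Type I error of 0.05 (2-sided), 90% power, sample size is only 27 DWI offenders per group"; "a sample size of 119 DWI offenders per group will allow for 90% power with a comparison of 0.44 to 0.36"; "We will adjust for an expected 15% attrition". With (z0.975 + z0.90)² = 10.507 and n = 10.507 × (1/m1 + 1/m2) / ln(m2/m1)²:

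- 4 v 2.4 events: 10.507 × 0.6667 / 0.2609 = 26.8, so 27.
- 4 v 3.2 events: 10.507 × 0.5625 / 0.04979 = 118.7, so 119. This is an exact 20% reduction; the rounded rates 0.44 and 0.36 would give 146 to 147.
- 119 / 0.85 = 140, below the 150 randomised; 150 × 0.85 = 127.5.

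Both stated sizes reproduce, and neither bears on H2. They fix the setting used below: 127 per arm, 4 control lockouts, rate ratio 0.8.

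**2. Size of the spurious path.** Let severity correlate r with family change and raise the log lockout rate by g per SD. If family change has no effect, its unadjusted coefficient is about r × g: −0.1 × 0.3 = −0.03, −0.2 × 0.5 = −0.10, −0.3 × 0.5 = −0.15. The simulated means were −0.03, −0.10 and −0.15. With an app effect a on family change, the spurious indirect effect is a × r × g. For a = 0.4 SD, r = −0.3 and g = 0.5 it is −0.06. Against a total effect of ln 0.8 = −0.223, that is 0.06 / 0.223 = 27% apparently mediated. At r = −0.1, g = 0.3 it is 0.012 / 0.223 = 5%. If a = 0, the product is zero whatever the confounding.

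**3. How often it reaches significance.** Each cell is 2,000 simulated trials with a true mediator effect of 0, a linear mediator model, a Poisson lockout model with robust variance, and a 95% Monte Carlo interval for the product of the two paths. Entries are the percentage of intervals excluding 0, unadjusted / adjusted for fully measured severity. Simulation error is at most √(0.25/2000) = 1.1 points.

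| r, g | a = 0 | a = 0.2 | a = 0.3 | a = 0.5 |
|---|---|---|---|---|
| −0.1, 0.3 | <1 / <1 | 3 / 1 | 7 / 3 | 14 / 6 |
| −0.2, 0.3 | 1 / <1 | 11 / 2 | 22 / 3 | 38 / 7 |
| −0.2, 0.5 | 3 / <1 | 20 / 1 | 37 / 4 | 60 / 6 |
| −0.3, 0.5 | 5 / <1 | 33 / 2 | 61 / 4 | 89 / 7 |

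With extra gamma overdispersion (0.5) at r = −0.2, g = 0.5, the unadjusted rates fall to 21% (a = 0.3) and 32% (a = 0.5).

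**4. At a = 0.4, with severity measured imperfectly.** This used 1,000 trials per setting and called mediation significant when both paths had |z| > 1.96, as a stand-in for the bootstrap. The unadjusted rate was 33% at r = −0.2, g = 0.3 and 80% at r = −0.3, g = 0.5. Weak confounding (−0.1, 0.3) gives about 9%. Adjusting for the baseline family score and a drinking measure that correlates 0.8 with severity reduces the 33% to 80% range to 9% to 27%. At a correlation of 0.6, 17% to 57% remain.

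**5. Direction, and which covariates are needed.** This check used the percentile bootstrap the plan intends, with 150 trials of 200 resamples, a = 0.4 and g = 0.5 (simulation error up to √(0.25/150) = 4 points).

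- Severity lowers family change only: 89% significant unadjusted, 5% adjusted for severity.
- Severity lowers the baseline score only, so that change includes regression to the mean: 53% significant in the opposite direction, 4% after adjusting for severity or for the baseline score.
- Both: 48% unadjusted, 92% adjusted for baseline family score alone, 5% adjusted for both.

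**6. Change score or 3-month score.** Write change D = M3 − M0. Once M0 is a covariate, D and M3 give the same app coefficient in the mediator model. In the lockout model, b·M3 + c·M0 = b·D + (b + c)·M0, so b is also the same. On the app-to-mediator path, with equal variances and correlation ρ between baseline and 3 months, the residual variance is σ²(1 − ρ²) against 2σ²(1 − ρ) for raw change. The ratio is (1 + ρ)/2, or 0.75 at ρ = 0.5.

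**The case against.** Three stronger readings are tempting, and the documents support none of them. First, a reader might infer that severity alone can produce significant mediation. It cannot: with the app-to-family path randomised, false mediation was at most about 5% when the app left family scores unchanged. Second, a reader might infer that the plan rules covariates out, or limits them to H1. It does not. The covariate step stands in the general analysis section after both hypotheses, its list is only by example, and the section on the study team's structure promises a more detailed analysis plan. What is established is that H2 covariates are not prespecified. Third, a reader might infer that the bias always favours finding mediation. The regression-to-the-mean case shows that it can also hide or reverse it.

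The size is also open to challenge. No document gives the app effect on family scores, the severity correlations or the log-rate slopes. Weak confounding yields rates not far above nominal, and overdispersion lowers them. The remedy is partial too: baseline drinking is self-reported by people at the start of probation, and a noisy measure leaves bias behind.

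All of this stands as a limit on strength and certainty. It does not answer the core point. Moving family scores is what the app is for, and in exactly that case the H2 test as specified cannot separate mechanism from severity.

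**Conclusion.** The point holds in conditional form. H2 relates lockouts to an unrandomised change in family scores and prespecifies no mediator–outcome confounders. If the app moves family scores, baseline severity can create, mask or reverse an indirect effect when family change has no effect on lockouts. At an assumed 0.4 SD app effect, the illustrative false-significance rate is about 9% to 80% depending on confounding strength, and lower with overdispersion. The percentages show what is possible and do not predict this trial. The primary comparison under H1 is unaffected.

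**What to change.** In the SAP, and in the matching protocol text, specify for H2:

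- In both the mediator regression and the lockout regression, include the baseline value of the mediator and baseline Form 90 drinking together. The baseline family score alone is not enough and can worsen the bias. State which Form 90 report (offender, CFM or both) is used. Use the baseline measure, since 3-month drinking comes after randomisation.
- With that adjustment, analysing change or the 3-month score given baseline is equivalent, so either may be written, and the precision gain follows.
- Add a sensitivity analysis showing how strong the remaining mediator–lockout confounding would have to be to remove the indirect effect.
- Word any mediation conclusion as conditional on no unmeasured confounding.
- Optionally add offender–CFM relationship and contact frequency, which section 3C.7.3 already adds to the demographics form. Their benefit was not tested here.

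The cost is SAP wording and a few lines of code. No new data, visits or participants are needed.
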